3.9 Post operative follow up

All patients included in this study will undergo orthopaedic review at the PHK Clinic or Midland Orthopaedic Clinic at 2-3 weeks, 6 weeks, 3 months, 1 year and 2 years following surgery. These are the routine follow-up time intervals for non-study patients undergoing TKA at PHK. Clinical and radiological outcomes of interest will be recorded by blinded observers using case report forms during these follow-up times (Appendix 19.1). The RP and fellow will assist in this.

3.10 Clinical and radiological assessment

The FJS, EQ5D-5L, OKS, VAS Pain, Likert scale, KOOS Jr and Kujala Anterior knee pain scores are validated tools for the clinical assessment of patients after knee arthroplasty (10,11,18,19). Each of these scores is completed preoperatively and then at regular intervals during follow-up (Appendix 19.1). This information is routinely discussed at each of these outpatient consultations but patients in this study will have the information recorded within these validated questionnaires to facilitate data analysis.

Routine clinical measures of height, weight, range of movement and pain description will be taken. To test endurance and strength, a 30 sec Sit to stand test will be measured. This test asks the participant to stand up / sit down from a standardised chair height within 30 seconds (Appendix 19.6). To measure the AP stability of the knee (20), a lachmeter reading will also be recorded at the post operative intervals and to measure strength, a hand

held dynamometer test will also be performed.

	Preoperative	Discharge	6 weeks	3 months	1 year	2 years
Patient demographics	X					
Patient medical history	X					
Operation details		X				
Clinical history and PROMS (FJS, EQ5D-5L, OKS, VAS pain, KOOS Jr, Kujala Anterior Knee Pain, Likert scale)	X		X (FJS and VAS only)	X	X	X
Functional Examination (Lachmeter testing, Range of Movement, Hand Held Dynamometer, 30s STS test)	X	X (range only)	X (range only)	X	X	X
Adverse Events	At occurrences through study period					

Table 1. Timelines for clinical data collection in all study patients.

	Preoperative	Discharge	6 weeks	3 months	1 year	2 years
Plain knee joint radiographs	X	X			X	X
Plain long-leg radiographs	X			X		
CT Knee joint	X					

Table 2. Timelines for radiological data collection in all study patients. Assessment windows will be as followed; 6 weeks review (± 1 week), 3 month review (± 2 weeks), 12 month review (± 2 months), 2 year review (± 2 months).

4.1 Study Timeline

Patients will be recruited from the private rooms at Perth Hip & Knee clinic. Based on the volume of TKAs performed and recruitment rates from previous studies within clinic, patients are expected to be recruited at a rate of 10 patients per month. The recruitment process will therefore take approximately 10-12 months from the start of the study. From the date of the operation, each patient will be followed-up for 24 months. A further six months will be required for data collection, analysis and dissemination of findings. The total duration of the study will therefore be 40 months.

4.2 Patient withdrawal criteria and procedure

All patients included into this study are free to withdraw from the study at any time without compromise to their future treatment. On withdrawal, patients will revert to the standard follow-up regimen for routine TKAs at the study site. The end of study form will be completed and the reason for withdrawal documented (Appendix 19.2). This form will also be completed if the patient is lost to follow-up or dies during the course of the study.

Enrolled patients will be withdrawn from the study if:

- The patient withdraws consent for participation in the study
- The patient is no longer able to comply with study instructions, attend scheduled appointments or complete questionnaires
- The patient undergoes implant revision

Data to the point of withdrawal will be used for analysis.

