6.3 Intention-to-treat population

The intention-to-treat (ITT) population is defined as all randomised patients assigned to either the mFA TKA or kFA TKA group, regardless of adherence with the entry criteria, regardless of the treatment they actually received, and regardless of subsequent withdrawal from treatment or deviations from the protocol. In the event that MA is converted to FA or vice versa intraoperatively, analysis will be performed using the ITT population and the treatment actually received by the patients. Intra-operative conversion from one method to another will however, be documented and presented/ published as part of the study.

In the event that there are errors in the randomization assignment, the analysis will be performed using the assigned treatment, not the treatment that the patient actually received. Any patient terminated early from the clinical trial will be included in the ITT population. All attempts will be made to collect complete follow-up evaluations for these patients despite study exit. These patients will be included in the analysis using univariate or multivariate-imputation methods.

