14.2 Reporting Incidents involving a medical device

Adverse device effects (complications) are defined as any of the following:

- a) Any device component failure (e.g. excessive migration of the implant or failure otherwise).
- b) Local complications arising from use of the TKA implants to include osteolysis, inflammation, local tissue reaction, periprosthetic fracture.
- c) Bone fracture during implantation
- d) Nerve damage arising from implant placement (as evidenced immediate postoperative by motor and/or sensory deficit not present preoperatively).
- e) Large vessel damage arising during surgery (with large blood loss, i.e. > 1500 ml).
- f) Prosthetic joint infection
- g) Surgical site infection
- h) Loosening of prosthetic components
- i) Other adverse events that are deemed device related and serious.

All serious adverse events, life-threatening problems, or deaths that occur during or following the use of the devices during the study should be fully documented in the research record by the Chief Investigator including the onset date, complete description of the event, severity, duration, action taken, and outcome. The event should be documented at the appropriate interval case report form. The Chief Investigator will be responsible for notifying the reviewing Research Ethics Committee, of any unanticipated adverse events according to local regulations.

The Chief Investigator will record all non-serious adverse events on the appropriate case report form.

Some adverse events may lead to subsequent surgical intervention. The surgical intervention should be reported separately from the presentation of the other adverse event. For example, if the adverse event is reported at the 3 months visit and a revision subsequently occurs after the 3 months visit, the revision should be reported in the next follow-up visit.

In the short term, revisions will usually occur due to acute/chronic infection, instability, and/or subject experiencing severe pain due to various causes. This data will be used in combination with clinical assessment, target history / examination and further investigation to determine likelihood of requiring revision.

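### Patients revised before two years fall out of the primary FJS comparison, and the plan does not secure their two-year score

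*Combined protocol and SAP*

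**What the plan says.** Section 4.2 lists events after which an enrolled patient is withdrawn. Besides withdrawal of consent there are two: "The patient undergoes implant revision" and "The patient is no longer able to comply with study instructions, attend scheduled appointments or complete questionnaires". It continues: "On withdrawal, patients will revert to the standard follow-up regimen for routine TKAs at the study site". On the data it says: "Data to the point of withdrawal will be used for analysis".

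Section 6.3 treats early exit differently. "Any patient terminated early from the clinical trial will be included in the ITT population", and "All attempts will be made to collect complete follow-up evaluations for these patients despite study exit". It then includes these patients by univariate or multivariate imputation, without naming a method.

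Section 6.2.1 makes the per-protocol analysis primary. Section 6.4 confines that population to patients who see the study through as the protocol lays down, and counts a secondary treatment among the possible violations. The End of Study form (Appendix 19.2) has a category for a removed implant. For withdrawn patients it asks about further contact for survivorship only.

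On causes, section 14.2 says that in the short term "revisions will usually occur due to acute/chronic infection, instability, and/or subject experiencing severe pain due to various causes".

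**The concern.** The primary outcome is the FJS at two years. A revised knee is one for which the first operation did not last, and two of the causes that section 14.2 names, instability and severe pain, could depend on alignment and balance, which is what the trial compares. If revised patients are absent, missingness on the primary endpoint is related to the outcome, and an arm with more revisions looks better than it is. Section 1.2 says that a move away from mechanical alignment would have to be justified by improved clinical outcomes. A comparison that leaves out revised knees is weak support for that.

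Site staff also have no clear instruction. Section 4.2 sends the patient back to routine care, while section 6.3 asks for full evaluations. A two-year score that is not collected cannot be recovered at analysis.

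**Working it through.** **Step 1. Follow one patient through the text.** Take a patient revised at 12 months.

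- Section 4.2: withdrawn, returned to routine follow-up, data used to that point.
- Sections 6.2.1 and 6.4: did not finish the study as planned, so not in the per-protocol population and not in the primary comparison. This holds whether or not an FJS is later obtained.
- Section 6.3: in the ITT population, with follow-up to be sought and imputation to be applied. If 4.2 is read strictly, the imputation can draw only on scores from before the revision.
- Appendix 19.2: no provision for further questionnaires.
- Section 14.2: a revision after the 3-month visit is to be reported at the next follow-up visit, which presumes that visits continue.

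**Step 2. The plan's own figures.** Section 3.5 enrols 100 patients 1:1, or 50 per arm, and needs 90 to complete, or 45 per arm. The 10% drop-out allowance in section 6.1 links the two: 90 / (1 − 0.10) = 100. The target difference is 12 FJS points (6.1). The allowance covers lost numbers. It does not address who is lost.

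**Step 3. Formula for the bias.** Let an arm have N patients, of whom k are revised and omitted. Let the others have mean m and the revised patients mean m − D. The mean over all N is m − kD/N, so omitting the revised patients raises the arm mean by kD/N. With equal N and D in both arms, the FA minus MA difference shifts by

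(k_FA − k_MA) × D / N.

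The primary analysis uses change from baseline (6.2.1). The formula is the same, with D read as the deficit in change.

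**Step 4. Numbers.** N = 45 to 50 comes from the plan. The revision counts and D = 20 to 60 points are assumptions.

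| Imbalance in revisions | Smallest shift (D = 20, N = 50) | Largest shift (D = 60, N = 45) | Share of 12 points |
|---|---|---|---|
| 0 | 0 | 0 | 0% |
| 1 patient | 20/50 = 0.4 | 60/45 = 1.3 | 3% to 11% |
| 3 patients | 60/50 = 1.2 | 180/45 = 4.0 | 10% to 33% |

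The top of the range is extreme. Against the one-year means of 59 and 75 in section 6.1, a 60-point deficit means scores of about −1 and 15. Three extra revisions is 6% of a 50-patient arm (3/50), and no source in the documents says how likely that is.

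**The case against.** The strongest reply is that the sections can be read together. Section 4.2 says what is kept. It does not say that later data are barred, so a reader who infers a flat contradiction with 6.3 is supplying the word *only*. Sections 3.6 and 5.0 refer the analysis of drop-outs to section 6, and 6.3 plainly expects exit to have happened. This stands: the passages are in tension and ambiguous, not proven incompatible.

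A reader might also infer that no two-year FJS will be collected after revision. The documents do not say so. Routine visits fall at the study times; section 3.9 says of them: "These are the routine follow-up time intervals for non-study patients undergoing TKA at PHK". But section 3.10 presents recording on the questionnaires as something done for study patients, where otherwise the content is discussed at consultation. Collection is possible but not secured.

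Nor does the text support the inference that an ITT analysis could not help. Section 6.3 provides for both later collection and imputation. The fair criticism is that the method is unnamed and, on a strict reading of 4.2, would have only pre-revision data to work from.

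It is also fair to say that the firm exclusion comes from 6.2.1 and 6.4 rather than from 4.2, so the point overlaps with the choice of a per-protocol primary analysis. That is right, and it shapes the fix. It does not remove the separate question of whether the score is collected at all.

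Finally, using the observed score after revision is one legitimate strategy among several; treating revision as failure is another. The plan should state which it follows.

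**Conclusion.** The point holds in this form. Patients revised before two years are absent from the primary FJS comparison through 4.2, 6.2.1 and 6.4 together, and nothing in 4.2 or the End of Study form ensures that their two-year score exists for any other analysis.

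The size is an illustration, not an estimate. It rests on assumed revision counts and deficits and on the same deficit in both arms. With balanced revisions and deficits the difference is unbiased, although both arm means are then too high. With an imbalance of one to three patients the shift runs from 0.4 to 4.0 points. It favours the arm with more revisions, and the documents do not show which arm that would be. A reader should not infer that the plan favours functional alignment.

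A reader might extend the argument to patients who cannot attend or complete questionnaires and say that they too are the worst outcomes. The documents do not show this: illness or relocation could be the reason, and someone truly unable to complete a questionnaire cannot supply a score under any rule. For them the point is narrower. Ending data collection because visits are missed is an avoidable loss.

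**What to change.** - **Section 4.2:** separate stopping study participation from stopping data collection. Only withdrawal of consent, death or true loss to follow-up should end FJS collection. After revision or missed visits, collect the FJS at 1 and 2 years, remotely if needed.
- **Sections 6.2.1 and 6.4:** state that revision does not remove a patient from the primary FJS comparison and that the observed score is used. Without this change, edits to 4.2 and 6.3 leave the exclusion in place.
- **Section 6.3:** match it to the new 4.2, and name the imputation method for scores that are still missing.
- **Appendix 19.2:** let the form record agreement to further questionnaires, not only to survivorship contact.
- **Analysis and reporting:** add one sensitivity analysis giving revised patients the worst score, and report the number of revisions by arm.

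The cost is protocol wording and a few extra questionnaires. The estimate will then include the consequences of revision, which should be said when it is reported.

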5.0 Consent

Patients with symptomatic knee osteoarthritis requiring TKA will be recruited from the private rooms at Perth Hip & Knee Clinic. All patients will be screened for eligibility based on the predefined inclusion and exclusion criteria (section 5.1) by a member of the clinical team. This includes the Orthopaedic Consultant Surgeon, Clinical Fellow, or Research Physio. If the patient meets the all of the inclusion criteria (section 5.1) and none of the exclusion criteria, and expresses an interest to participate in the study they will be provided with a patient information sheet (Appendix 19.7). This provides details about the study, treatment, follow-up and contact details for further information. All members of the clinical team are familiar with the study and will address any preliminary questions about the study. Details of those patients expressing an interest to participate in the study will be recorded in the patient contact sheet, which will be a password protected excel document that only [name], [name] and [name] will have access to.

One week after this outpatient consultation, the Research Physiotherapist will telephone the patient to answer any additional queries and confirm whether or not the patient would like to participate in the study. If the patient agrees to participate in the study, the Research Physiotherapist will randomise the patient into one of the two treatment groups. Patients allocated to mFA TKA will form the ‘control group’ whilst those allocated to kFA TKA will form the ‘investigation group’. The method for randomisation is discussed in Section 3.6. Written informed consent for both the operative procedure and inclusion into the study will be signed at the preadmission appointment.

The ideal length of time between initial consultation and obtaining informed consent for inclusion into the study is at least 1 week. This method provides time for potential participants to consider the trial and ask questions before written consent for participation is requested. This time may be shortened due to patient flow and clinic appointment availability, as long as the patient is agreeable. Consent will be taken by the study coordinator or by

a designated member of the surgical team who is familiar with the study.

If the patient initially agrees to participate in the study and then changes his/her mind at a later stage, they are free to do so without any compromise to their further care. If this occurs before obtaining informed consent then the patient's decision will be relayed to the Operating Surgeon who will discuss suitable options directly with the patient, and organise postoperative follow-up care as per all routine (non-study) patients undergoing TKA at Perth Hip & Knee Clinic. If the patient agrees to participate in the study and then declines further inclusion after surgery has been performed then the patient's follow-up care will be arranged as per routine TKA follow up. Statistical analysis of patients that drop out is discussed in section 6. Following randomisation and informed consent, baseline information will be recorded and documented in the baseline investigator form (Appendix 19.1). Data handling and management are recorded in more detail in section 9.

Being able to provide informed consent to the study is of paramount importance. Therefore, patients who lack the capacity to provide this, for example patients with dementia, will not be considered for the study. It is also important to the data collection scheme that patients are able to follow commands, read and interpret questions via questionnaires. Those who cannot hear, read or understand English, will not be considered for the study.

Participants will not receive any preferential treatment or payment for taking part in the study.

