3.4 Study population and groups

Patients with symptomatic knee osteoarthritis requiring TKA will be recruited from the [name] and [name] private rooms at Perth Hip & Knee Clinic. All patients will be screened for eligibility based on the predefined inclusion and exclusion criteria (section 5.1). Patients interested in participating in the study will be provided with an information leaflet and contact telephone number for further information (Appendix 19.7). Details of those patients expressing an interest to participate in the study will be recorded and then be forwarded to the Research Physiotherapist.

The Research Physiotherapist will telephone or meet with the patient to answer any additional queries and confirm whether or not the patient would like to participate in the study. More complex queries will be escalated to the Chief Investigator who will telephone the patient directly to discuss these issues further. Ideally, the time frame from the orthopaedic consultation to the decision to participate in the study will be approximately one week, which will give the patient sufficient time to perform further research, discuss study participation with family and/or friends, and contact the Research Physiotherapist for any additional information. This time frame may be shortened if a patient is agreeable with the study, due to patient flow and appointment availability at the consulting rooms. Contact details of the Research Physiotherapist and Chief Investigator are provided within the patient information leaflet.

If the patient agrees to participate in the study, the Orthopaedic fellow will randomise the patient into one of the two treatment groups. Patients allocated to mFA TKA will form the 'control group' whilst those allocated to kFA TKA will form the 'investigation group'. The method for randomisation is discussed in section 3.6. Written informed consent for both the operative procedure and inclusion into the study will be signed at the preadmission visit (Appendix 19.7). The procedure for obtaining written informed consent is discussed in more detail in section 5.

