3.5 Sample Size In total, 100 patients will be enrolled in a 1:1 ratio between the two treatment groups. This will ensure that the minimum of 90 patients required to answer the study question are followed up for the duration of the study. The enrolment goal is to have at least 45 patients in each of the two treatment groups completing the study. Sample size calculation and statistical analysis are more comprehensively detailed in section 6.

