3.6 Randomisation procedure

The system for randomisation will be the same throughout the study period and must be strictly adhered to. The following method will be used to allocate a trial patient to either the mFA TKA ('Control group') or to the kFA TKA ('Investigation group').

Randomisation will be carried out using a blocked effect. This method is designed to randomize subjects into two groups that result in equal sample sizes over time. The blocks will be small (n=4), and balanced within the predetermined group assignments, which will keep the number of subjects in each group similar at all times. There will be no stratification factors involved in the randomization as randomization will occur before the trial starts. Using a randomization website (www.random.org), a random number (between 1 and 100000) will be generated. This will form the "seed" number for the blocked randomization process. Using a randomization website (www.sealedenvelope.com) the randomization list will be created. Patients will be allocated in a sequential order of consent, strictly adhering to the allocation of groups. Screen shots of the randomization process and seed number will be taken throughout, and held from the CI to minimize randomization bias. The orthopedic fellow will then privately communicate to the CI the allocated group, to enable alignment and templating planning to be performed using the MAKO software. All patients and clinical staff recording the post operative clinical outcomes of interest will remain blinded to minimize performance and detection bias.

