If the patient initially agrees to participate in the study and then changes his/her mind at a later stage, they are free to do so without any compromise to their further care. If this occurs before obtaining informed consent then the patient's decision will be relayed to the operating surgeon who will discuss suitable options directly with the patient, and organise postoperative follow-up care as per all routine (non-study) patients undergoing TKA at Perth Hip and Knee Clinic. There randomisation number will not be reallocated to the next patient, to ensure the blocks remain concealed. Drop in and out details are in section 6. If the patient agrees to participate in the study and then declines further inclusion after surgery has been performed, then the patient's follow-up care will be arranged as per routine TKA follow up at Perth Hip and Knee Clinic. Patients will be notified that once statistical analysis of the study has been performed, and all patient data has been de-identified for analysis, they will not be able to withdraw their clinical data. Statistical analysis of patients that drop out is discussed in section 6. Following randomisation and informed consent at the preadmission visit, baseline information will be recorded and documented in the Perth Hip and Knee Clinic Socrates database. Data handling and management are recorded in more detail in section 9.

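### Sections 3.4 and 5.0 randomise on verbal agreement, before written consent and baseline; other sections point to a different order, and two different randomisers are named

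*Combined protocol and SAP*

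**What the plan says.** Two sections describe recruitment in the same sequence. Section 5.0, after a telephone call to confirm interest, states: "If the patient agrees to participate in the study, the Research Physiotherapist will randomise the patient into one of the two treatment groups". Section 3.4 makes the same step follow the patient's agreement, but there "the Orthopaedic fellow will randomise the patient into one of the two treatment groups". Section 3.4 then adds: "Written informed consent for both the operative procedure and inclusion into the study will be signed at the preadmission visit". Section 5.0 also puts the signature at the preadmission appointment.

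Section 3.6 deals with a patient who changes their mind before giving informed consent: "There randomisation number will not be reallocated to the next patient". Sections 3.6 and 5.0 both have baseline recorded once randomisation and consent are done; section 6.5 says only that it follows the consent form.

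Other wording suggests a different order. Section 3.6 says: "Patients will be allocated in a sequential order of consent". Section 3.7 mentions informed consent ahead of randomisation when it describes the route to surgery.

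On knowledge of the arm, section 3.6 says: "The orthopedic fellow will then privately communicate to the CI the allocated group", so that planning can start. Its blinding statement reads: "All patients and clinical staff recording the post operative clinical outcomes of interest will remain blinded". Under section 5.0, consent is taken by the study coordinator or a designated member of the surgical team.

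**The concern.** Allocation concealment should last until the patient is irrevocably in the trial. If the arm is known to staff while the patient can still say no, those staff can affect, even without meaning to, who goes on to sign. Randomisation does not protect against that loss, because it happens afterwards and may differ by arm.

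Two further matters follow. Baseline measured after allocation can be coloured by knowledge of the arm, and section 6.2.1 analyses each patient's difference from baseline. And someone randomised who never consents has no clear place in the analysis: section 6.3 counts them in the ITT population, yet no data on them can be used.

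**Working it through.** There is no figure in the plan to reproduce here, so the check is a comparison of the text.

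**1. Order of consent and randomisation**

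| Section | Order stated or implied | Randomiser |
|---|---|---|
| 3.4 | agreement, randomisation, written consent at preadmission | Orthopaedic fellow |
| 5.0 | agreement by telephone, randomisation, written consent at preadmission | Research Physiotherapist |
| 3.6, allocation text | allocation follows the order of consent (written or verbal not specified) | fellow passes on the result |
| 3.6, withdrawal text | a patient can hold a number before consent | not stated |
| 3.7 | consent named before randomisation | not stated |

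The retired-number rule in section 3.6 helps decide between these. A rule on what happens to the number of someone who leaves before consent is needed only if numbers can be issued before consent. It therefore supports the order in sections 3.4 and 5.0. The contrary phrases in sections 3.6 and 3.7 do not say that written consent must come first.

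**2. Alternative reading.** The baseline sentence in section 3.6 could mean that randomisation itself takes place at the preadmission visit. That would shorten the gap. It would not change the position of baseline, which sections 3.6 and 5.0 still place after randomisation.

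**3. Who can know the arm before the signature.** For the fellow this is explicit, since the fellow tells the Chief Investigator. For the Research Physiotherapist it is an inference from performing the randomisation. The Chief Investigator knows once told. A surgical team member may take consent, and the blinding statement covers only patients and those who record postoperative outcomes. Nothing in the text available for review, which does not include sections 3.2 and 3.3, keeps the person taking consent or recording baseline unaware of the arm.

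**4. Which baselines are exposed.** The Forgotten Joint Score is a tick-box questionnaire (Appendix 19.5). Section 5.1 requires patients to be able to complete such measures on their own, and patients are blinded. Range of movement, Lachmeter, dynamometer and chair-stand results (section 3.10) are measured or scored by staff and are more open to influence.

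**5. Analysis sets for a patient who declines after allocation**

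- ITT (section 6.3): included, because the population is everyone randomised. The imputation rule there is written for patients who leave the trial early, and section 4.2 uses data up to withdrawal. Neither fits a person with no consent, no baseline and no outcome.
- Per-protocol (sections 6.2.1 and 6.4, the primary analysis): excluded, because the patient does not complete the study.

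**6. Size.** The documents give neither the proportion who decline between agreement and signature nor the time between the two. The bias cannot be calculated.

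**The case against.** The best defence is that sections 3.4 and 5.0 refer to section 3.6 for the method, and section 3.6 allocates in order of consent, with section 3.7 in agreement. On that view the intended order is consent first and the recruitment text is loosely drafted. This shows that the plan contradicts itself; it does not remove the problem, because sections 3.4 and 5.0 are what recruiting staff would follow and the retired-number rule fits them.

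Several stronger readings are tempting, and the documents do not support them.

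- A reader might infer that the primary endpoint is biased through its baseline. Self-completion by blinded patients makes a large effect unlikely.
- A reader might infer that patients choose according to their arm. Patients are meant to stay blinded, so the route is staff influence.
- A reader might infer that retired numbers use up the drop-out margin. No passage defines enrolment, but section 3.5 speaks of patients enrolled, the letter in Appendix 19.3 pairs consent with an enrolment date, and section 3.6 sends those who decline before consent to routine non-study care. These point to a target of 100 consented patients, so a loss of power is not shown.
- A reader might infer that decliners vanish unreported. Unwillingness to sign is an exclusion criterion in section 5.1, and section 6.4 lists protocol violators with reasons. That partly covers the per-protocol set; the ITT gap remains.

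The missing team description also limits the point about who is unaware of the arm to the text that can be read.

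**Conclusion.** The concern holds as a contradiction with a real consequence. Two sections allow allocation before written consent, a third confirms that a number can exist at that stage, baseline follows allocation, and the randomiser is not the same role in sections 3.4 and 5.0. As written, staff who know the arm could influence who signs. The ITT population can include people about whom nothing may be analysed.

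The direction and size of any selection are unknown, and nothing in the documents shows that selection occurred. The conclusion assumes that staff follow sections 3.4 and 5.0 as worded, and that sections 3.2 and 3.3 contain no rule separating the randomiser from consent. The change should be made because it protects concealment at little cost; it is not a finding that the primary result is invalid. Whether those who record outcomes are truly blinded, given that section 3.9 has the Research Physiotherapist and fellow assisting, is a separate question that the fix only touches.

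**What to change.** State one order in sections 3.4, 3.6, 3.7 and 5.0: eligibility confirmed, written consent signed, baseline recorded, randomisation, then notice to the Chief Investigator. Name one existing role as randomiser, the same in every section, and require that this person does not take consent or record baseline or outcomes for that patient. Because both roles now named also assist with outcome recording, whichever is chosen must be released from that task for the patients they randomise. No additional staff are needed.

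The ITT population can then stay as everyone randomised, all of whom will have consented.

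For patients already randomised, report by arm how many never gave written consent, and tabulate the randomisation date (a field on the preoperative case report form) against the date on the consent form. If those patients are left out because no data can be used, call the set a modified ITT and state the exclusion as a limitation: it conditions on the very step that staff could have influenced.

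The costs are redrafting, one tabulation and less time between allocation and surgery. Section 3.7 eases the last, since mechanical and kinematic plans are both prepared from the CT scan, but section 3.6 and Appendix 19.9 tie planning to the allocation. The interval from preadmission to surgery is not given, so the sponsor should confirm that it is enough. The benefit for patients already recruited is limited: this version is dated 14/10/2021 and the study summary expects recruitment to finish in 12/2021, so for many patients only the reporting part may apply.
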